6.2.2.3 Final study analysis

A final analysis of the data will occur after all infants have completed the study and will include data from infants enrolled in the pilot study.

All proportions specified below in the objectives will be compared by group (unvaccinated group or vaccinated group) using a Mantel-Haenszel statistic in a stratified analysis by site (i.e. Duke, UNC and CCHMC) to control for the randomization blocks at the two-sided alpha 0.05 level unless otherwise specified. The odds ratio and corresponding 95% confidence interval will also be calculated and presented. There will be no adjustment to the alpha level made for the secondary and exploratory objectives.

Primary Objective 1 - To compare proportions of preterm infants with apnea in a 48-hour monitoring period after vaccination in the “vaccinated” group versus a 48-hour monitoring period after randomization in the “unvaccinated” group.

The proportion of infants with ≥ 1 apneic event apnea (as defined in Section A.5.3) will be presented for each group and compared using a Mantel-Haenszel statistic.

Secondary Objective 1 - To compare the clinical importance of apneic events in a 48-hour monitoring period after vaccination in the “vaccinated” group versus a 48-hour monitoring period after randomization in the “unvaccinated” group.

For this objective we will present the proportions of infants in each group who required increase in respiratory support (as defined in Section A.5.3) and compare these proportions using a Mantel-Haenszel statistic. We will also report summary statistics regarding the number of distinct episodes and the duration of episodes, including mean, median, standard deviation, interquartile range, and range. We will compare the number of distinct episodes of apnea and the duration of episodes between groups using the Wilcoxon rank sum test.

Secondary Objective 2 - To compare proportions of preterm infants with severe cardiorespiratory events in a 48-hour monitoring period after vaccination in the “vaccinated” group versus a 48-hour monitoring period after randomization in the “unvaccinated” group.

For this objective we will present the proportion of infants in each group experiencing a severe cardiorespiratory event (as defined in Section A.5.3) or received positive pressure ventilation at least once during the 48 hours after randomization/vaccination and compare these proportions using a Mantel-Haenszel statistic.

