### **3.2 Secondary**

- a)
  - 1. SOM 1.1: Average number of apneic episodes in a 48-hour monitoring period after vaccination in the “vaccinated” group and a 48-hour monitoring period after randomization in the “unvaccinated” group.
  - 2. SOM 1.2: Average duration of apneic episodes in a 48-hour monitoring period after vaccination in the “vaccinated” group and a 48-hour monitoring period after randomization in the “unvaccinated” group.
  - 3. SOM 1.3: Proportion of infants requiring any increase in respiratory support in a 48-hour monitoring period after vaccination in the “vaccinated” group and a 48-hour monitoring period after randomization in the “unvaccinated” group.
- b)
  - 1. SOM 2.1: Proportion of infants with  $\geq 1$  severe cardiorespiratory event in a 48-hour monitoring period after vaccination in the “vaccinated” group and a 48-hour monitoring period after randomization in the “unvaccinated” group.
  - 2. SOM 2.2: Proportion of infants requiring positive pressure ventilation in a 48-hour monitoring period after vaccination in the “vaccinated” group and a 48-hour monitoring period after randomization in the “unvaccinated” group.

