### 4.2 Sample Size and Power

The study has approximately 84.3% power to reject the null hypothesis of no difference in the proportion of infants with apnea in the “vaccinated” group compared to the “unvaccinated” group based on a two-side alpha 0.05 chi-square test with N=135 per group. This assumes that the proportion of infants with apnea will be 15% in the “unvaccinated” group and 2-fold higher (30%) in the “vaccinated” group. This assumption is based on a review of the literature and expert opinion. The study allows for a 10% dropout rate to give a total sample of 300 infants.

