**Figure 1. Intent-to-Treat (ITT) Analysis**

**6.2 Modified Intent-to-Treat (mITT) population (Figure 2)**

- a) **Definition:** The definition is the same for the ITT and mITT. The mITT population includes any infant that was enrolled and randomized in the study.
- b) **Analysis:** For the mITT analysis, infants will be analyzed in their assigned treatment arms irrespective of receipt of vaccine. Study outcomes will be included in the analysis as follows:
  - i) **Vaccinated group:** study outcomes in the 48-hour monitoring after vaccination. If vaccination does not occur by 12 hours after randomization, then study outcomes will be assessed between 12 and 60 hours after randomization.
  - ii) **Unvaccinated group:** study outcomes in the 48-hour monitoring period after randomization. This is the same for the IIT and the mITT populations.

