### 8.1 Primary Objective

The primary objective (**PO-1**) of the study is to compare proportions of preterm infants with apnea in a 48-hour monitoring period after vaccination in the “vaccinated” group versus a 48-hour monitoring period after randomization in the “unvaccinated” group.

- *Research hypothesis: the proportion of infants with apnea will be higher in the “vaccinated” group compared to the “unvaccinated” group.*

The proportion of infants with ≥1 apneic event will be presented for each group and compared using a Mantel-Haenszel statistic in a stratified analysis by study site and gestational age to control for the randomization blocks at the two-sided alpha 0.05 level. The stratified odds ratio and corresponding 95% confidence interval for the occurrence of apnea will also be calculated.

Apnea will be defined as a pause in respirations of >20 seconds, or a pause in respirations of >15 seconds with associated bradycardia (heart rate <80 beats per minute), obtained from the cardiorespiratory monitor. Presence of ≥1 apneic event will be counted as positive (1) for this analysis and no apnea reported will be negative (0). Apneic events identified by the

cardiopulmonary monitor will be confirmed during manual blinded review via an agreed-upon review process. Apneic events determined by the monitor must also be confirmed by manual review to be counted as apnea for the primary analysis. If these events are NOT by manual review, then they are not counted as apnea for the primary analysis. However, events without supporting cardiorespiratory monitoring strips, that cannot be manually reviewed, will also be counted as apnea for the primary analysis.

No adjustments will be made to the alpha level (two-sided  $\alpha=0.05$ ) for the primary objective.

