## 8.2 Secondary Objectives

There are two secondary objectives for this study.

- a) The first secondary objective (**SO-1**) is to compare the clinical importance of apneic events in a 48-hour monitoring period after vaccination in the “vaccinated” group versus a 48-hour monitoring period after randomization in the “unvaccinated” group.

There are 3 secondary outcome measures (SOM) for this objective. For SOM 1.1, the average number of apnea events in each group will be presented and the number of apnea events will be compared using a Poisson regression model with study site and gestational age as covariates to control for the randomization blocks. Summary statistics regarding the number of distinct apnea episodes and the duration of episodes, including mean, median, standard deviation, and range will be reported by group and site.

For SOM 1.2, the average duration of apnea episodes between groups will be compared using a mixed effects model (Robinson 2007) with a random intercept for each infant with one or more events and study site and gestational age as covariates to control for the randomization blocks. Apneic events will be identified using the same criteria for primary objective.

For SOM 1.3, the proportion of infants requiring an increase in respiratory support will be presented and compared using a Mantel-Haenszel statistic in a stratified analysis by site and gestational age to control for the randomization blocks at the two-sided  $\alpha 0.05$  level. The stratified odds ratio and corresponding 95% confidence interval for the occurrence will also be calculated. These tests will be performed at the  $\alpha 0.05$  level.

Increase in mode of respiratory support will be defined as (a) progression from any lower level at baseline (at time of randomization in the unvaccinated group and vaccination in the vaccinated group) to any higher level, as well as (b) any increase in nasal cannula flow rate, or continuous positive airway pressure (CPAP).

- b) The subsequent secondary objective (**SO-2**) is to compare proportions of preterm infants with severe cardiorespiratory events in a 48-hour monitoring period after vaccination in the “vaccinated” group versus a 48-hour monitoring period after randomization in the “unvaccinated” group.

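### SOM 1.2 tests apnea duration only among infants who had apnea, so its between-arm difference and p-value cannot be read as an effect of vaccination on duration

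*SAP*

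**What the plan says.** - **Endpoint.** SAP 3.2 lists "SOM 1.2: Average duration of apneic episodes in a 48-hour monitoring period after vaccination" in the vaccinated group, with the matching window after randomization in the unvaccinated group. It serves SO-1, which is to "compare the clinical importance of apneic events in a 48-hour monitoring period after vaccination" between arms.
- **Model.** SAP 8.2 uses a mixed effects model with "a random intercept for each infant with one or more events". Adjustment is limited to the stratification factors, which enter the model as follows: "study site and gestational age as covariates to control for the randomization blocks". No other adjustment is given.
- **Population.** SAP 6.4 makes mITT the primary population for all objectives, and SAP 6.2 says "The mITT population includes any infant that was enrolled and randomized in the study".
- **Expected effect on having apnea.** SAP 8.1 hypothesizes that "the proportion of infants with apnea will be higher in the" vaccinated group. SAP 4.2 sizes the trial for 15% versus 30%.
- **Protocol.** Section 6.2.2.3 names a different method: "We will compare the number of distinct episodes of apnea and the duration of episodes between groups using the Wilcoxon rank sum test". It gives no rule for infants without apnea.
- **Elsewhere.** SAP 8.4 treats SO1 as count data by postmenstrual-age group. SAP 9 varies event adjudication and excludes infants with certain procedures or injections. Neither addresses the restriction to infants with events, and nothing labels SOM 1.2 as conditional or descriptive.

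**The concern.** An infant with no apnea has no episode duration, so the SOM 1.2 model contains only infants who had an event after randomization. That status is the primary outcome. If vaccination changes it, the vaccinated and unvaccinated infants in the model are no longer the groups that randomization made comparable.

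Site and gestational age are baseline factors. They do not identify which vaccinated infants would have had no apnea without vaccine. The random intercept accounts for repeated episodes within an infant, not for which infants enter the model.

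SO-1 is meant to inform clinicians about the clinical importance of apnea. A significant difference in duration, in either direction, could be reported as something the vaccines do to episodes when it reflects only a different mix of affected infants.

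**Working it through.** **Inputs from the plan (SAP 4.2).** 135 per arm, 15% versus 30% with apnea, two-sided alpha 0.05, stated power 84.3%, total 300 after 10% dropout.

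**The plan's own figure.** Chi-square test, pooled variance under the null, no continuity correction:
- pooled proportion = (0.15 + 0.30)/2 = 0.225
- null SE = √(2 × 0.225 × 0.775/135) = 0.0508
- alternative SE = √((0.15 × 0.85 + 0.30 × 0.70)/135) = 0.0500
- z = (0.15 − 1.96 × 0.0508)/0.0500 ≈ 1.01, power ≈ 84.3%
- 270/0.90 = 300

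Both figures reproduce. No power or effect size is stated for SOM 1.2.

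**Who enters the SOM 1.2 model.** Unvaccinated: 135 × 0.15 = 20.25. Vaccinated: 135 × 0.30 = 40.5. If vaccination prevents apnea in no infant, about half of the vaccinated infants in the model (20.25 of 40.5) have no counterpart among the unvaccinated infants in it.

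**Size of the bias, by mixture.** Assume a mean duration of 25 s in the 15% who would have apnea in either arm, with no vaccine effect on them. Let the added 15% have mean m. Then:

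vaccinated mean = (0.15 × 25 + 0.15 × m)/0.30

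The last two columns simulate a random-intercept model on infants with events (300 trials per row, 135 per arm). Assumptions: SD 3 s between and 4 s within infants; on average 3 events in the first 15% and 1.5 in the added infants; arm as the only covariate.

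| m (s) | Vaccinated mean (s) | Apparent difference (s) | Model estimate (s) | p < 0.05 |
|---|---|---|---|---|
| 18 | 21.5 | −3.5 | −3.2 | 68% |
| 20 | 22.5 | −2.5 | −2.3 | 46% |
| 22 | 23.5 | −1.5 | −1.4 | 23% |
| 25 | 25.0 | 0 | −0.1 | 4% |
| 28 | 26.5 | +1.5 | +1.2 | 17% |

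With 300 trials the simulation error is at most about 3 points: √(0.46 × 0.54/300) = 0.029.

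**Sensitivity to the assumed durations.** Normal durations can fall below the limits in the apnea definition (more than 20 s, or more than 15 s with bradycardia), so further simulations put a 15 s floor on episodes.
- 30 s versus 22 s: significant shortening in 69% (normal, SDs 4 s and 5 s), 67% (15 s floor) and 23% (15 s floor with strong skew, log-scale SDs 0.6 and 0.7).
- 25 s versus 22 s: 12% with the floor, 11% with floor and skew.
- Equal means: no excess beyond chance.
- Added infants at 28 s against 25 s, with the floor: significantly longer in 20%.

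**A measure defined for every infant.** Take total apnea seconds, 0 if none, with the event counts of the table. Unvaccinated mean = 0.15 × 3 × 25 = 11.25 s per infant. The added infants contribute 0.15 × 1.5 × m = 4.05, 4.50 or 4.95 s for m = 18, 20 or 22. The vaccinated means are 15.30, 15.75 and 16.20 s. The sign is the reverse of the conditional comparison.

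**Limits of that measure.** Total time is zero for 70% to 85% of infants. In two sets of simulations, a rank test on it agreed with the primary test on significance in 93% to 100% of trials. With 15% incidence in both arms and mean duration raised from 25 s to 35 s, the rank test rejected in 4% and 6% of trials in the two sets, and the mixed model in 100% in both.

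**The case against.** The best defence is that the restriction belongs to the endpoint. Episode duration does not exist without an episode, and asking what episodes are like when they occur is a fair clinical question. The model is a reasonable way to describe that. What fails is its use as a between-arm test with no conditional label.

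A second defence is that POM 1.1, SOM 1.1 (event count), SOM 1.3, SOM 2.1 (which includes pauses over 30 s) and SOM 2.2 are defined for all randomized infants and will be reported beside it. This stands and limits the harm, because a misleading duration result would seldom be read alone. It does not make the SOM 1.2 p-value interpretable as a vaccine effect.

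A reader might go further and infer that SOM 1.2 will make vaccination look reassuring. The documents do not support that. They give no episode durations, and the bias disappears or reverses when the added infants have equal or longer episodes.

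A reader might also infer that total apnea time should replace SOM 1.2. It should not: a rank test on it would almost always miss a true lengthening at equal incidence, which the conditional model detects.

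Nor does the protocol contain the same restriction. Its Wilcoxon sentence is silent on infants without apnea. It shows only that the two documents name different methods.

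**Conclusion.** The point holds in limited form. The SOM 1.2 comparison is not a randomized comparison, and its estimate and p-value combine an effect on duration with a change in who has apnea. Selection at the plan's own rates is substantial, about 20 versus 40 infants.

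The bias in seconds and the false-positive rates rest on assumed durations, SDs and event counts. False shortening was significant in about 12% to 70% of simulated trials when the added infants had shorter episodes. There was no excess when episodes were equal, and false lengthening in about 17% to 20% when theirs averaged 28 s against 25 s. The reasoning also takes the expected rise in apnea as given. If vaccination does not change which infants have apnea, this selection does not arise.

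The primary analysis is unaffected. The change should be made because it is nearly free and prevents an unsupported conclusion under SO-1.

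**What to change.** 1. In SAP 8.2, state that the SOM 1.2 mixed-model estimate is conditional on having apnea. Report it with a 95% CI as a descriptive summary, not as a test of vaccine effect, and interpret it only beside POM 1.1, SOM 1.1 and SOM 2.1.
2. Add, as a supplement, a duration-based measure defined for every randomized infant, such as total apnea seconds or longest pause in the 48-hour window, 0 if none. Present it by arm with a comparison stratified by site and gestational age (for example van Elteren).
3. State the downside in the SAP: a rank test on total time largely repeats the primary test and has almost no power for longer episodes at equal incidence, so the conditional duration estimate must still be shown.
4. Reconcile the Wilcoxon test in Protocol 6.2.2.3 with the SAP model, and record the change in the SAP version table.

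The cost is a few sentences and one short program. Protocol 5.4 already has the date, time and duration of each event recorded, so no new data are needed.

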### 8.3 Exploratory Objectives

There are three exploratory objectives for this study.

- a) The first exploratory objective (**EO-1**) is to compare proportions of preterm infants with temperature instability in a 48-hour monitoring period after vaccination in the “vaccinated” group versus a 48-hour monitoring period after randomization in the “unvaccinated” group.

For this objective we will present the proportion of infants in each group experiencing fever (temperature  $\geq 38^{\circ}\text{C}$ ) (EOM 1.1) and the proportion in each group experiencing hypothermia (temperature  $< 36^{\circ}\text{C}$ ; as defined in **Section 5.4**) (EOM 1.2) at least once during the 48 hours after randomization/vaccination. These proportions (fever and hypothermia) will be compared using a Mantel-Haenszel statistic in a stratified analysis by study site and gestational age to control for the randomization blocks. The stratified odds ratio and corresponding 95% confidence interval for the occurrence of fever and hypothermia will also be calculated.

- b) The second exploratory objective (**EO-2**) is to compare event counts and proportions of preterm infants with other clinically important adverse events in a 48-hour monitoring period after vaccination in the “vaccinated” group versus a 48-hour monitoring period after randomization in the “unvaccinated” group.

For this objective the number of oxygen desaturation events (EOM 2.1) and the number of bradycardia events (EOM 2.2) will be presented using summary statistics regarding the number of distinct events and the duration of events, including mean, median, standard deviation, and range will be reported by group and site. The number of events for each outcome will be compared using a Poisson regression model with study site and gestational age as covariates to control for the randomization blocks.

The proportion of infants in each group experiencing other clinically important adverse events (infants requiring blood culture and/or antibiotics (intravenously or intramuscularly) in the setting of blood culture for sepsis evaluation (EOM 2.3) and infants with a serious adverse event (SAE; EOM 2.4; protocol section 5.4) at least once during the 48 hours after randomization/vaccination will be presented. These

proportions will be compared using a Mantel-Haenszel statistic in a stratified analysis by study site and gestational age to control for the randomization blocks. The stratified odds ratio and corresponding 95% confidence interval for the occurrence of these outcome measures will also be calculated. We will provide a listing of SAE narratives and relatedness descriptions.

- c) The third exploratory objective (**EO-3**) is to compare clinically important adverse events occurring between 48 hours and 14 days after vaccination among infants in the vaccinated group who do / do not have apnea in a 48-hour monitoring period after vaccination.

For this objective the proportion of infants in the vaccinated group with and without apnea in a 48-hour monitoring period who experience each of the clinically important adverse events listed below at least once between 48 hours and 14 days after vaccination will be presented.

- $\geq 1$  episode of clinical apnea in hospitalized infants (EOM 3.1)
- any increase in respiratory support in hospitalized infants (EOM3.2)
- blood culture and/or antibiotics (intravenously or intramuscularly) in the setting of blood culture for sepsis evaluation in hospitalized infants (EOM 3.3)
- positive pressure ventilation in hospitalized infants (EOM 3.4)
- readmission to the hospital within 14 days of vaccination in discharged infants (EOM 3.5)

These subgroup comparisons will be made using a Mantel-Haenszel statistic in a stratified analysis by study site and gestational age to control for the randomization blocks at the two-sided alpha 0.05 level. The stratified odds ratio and corresponding 95% confidence interval for the occurrence of these outcome measures will also be calculated.

No adjustments will be made to the alpha level (two-sided alpha=0.05) for these exploratory analyses.

#### **8.4 Postmenstrual age (PMA) Evaluation**

Study objectives PO1, SO1, SO2, EO2.1, EO2.2, EO3.1, and EO3.2 will be presented and evaluated between groups by postmenstrual age group (PMA <37 weeks /  $\geq$ 37 weeks). PMA will be defined as the sum of gestational age plus postnatal age. PO1, SO2, and EO3 are categorical with either no event or 1 or more events, and will be presented and compared using a Mantel- Haenszel statistic by PMA group at the two-sided alpha 0.05 level. The stratified odds ratio and corresponding 95% confidence interval for the occurrence will also be calculated. SO1 and EO2 are count data and will be compared using a Poisson regression model with study site as covariates by PMA group. These tests will be performed at the alpha 0.05 level.

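### SAP 8.4 leaves gestational age out of its count models by postmenstrual age (PMA) group and plans no estimate of whether the arm effect differs by PMA

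*SAP*

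**What the plan says.** SAP 8.4 opens: "Study objectives PO1, SO1, SO2, EO2.1, EO2.2, EO3.1, and EO3.2 will be presented and evaluated between groups by postmenstrual age group", with the cut at 37 weeks. It assigns a Mantel-Haenszel statistic by PMA group to PO1, SO2 and EO3, and adds: "The stratified odds ratio and corresponding 95% confidence interval for the occurrence will also be calculated". It does not name the strata. For the rest, "SO1 and EO2 are count data and will be compared using a Poisson regression model with study site as covariates by PMA group". All tests are at 0.05. No interaction term, homogeneity test or ratio of effects is mentioned.

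The main analyses are more specific. Randomization is stratified by site and gestational age (<28, ≥28 weeks; SAP 4.3). In SAP 8.3, EOM 2.1 and EOM 2.2 are "compared using a Poisson regression model with study site and gestational age as covariates to control for the randomization blocks", and SAP 8.2 does the same for SOM 1.1. SAP 8.2 gives SO1 two further measures. For SOM 1.2, "the average duration of apnea episodes between groups will be compared using a mixed effects model" "with a random intercept for each infant with one or more events". The other reads: "For SOM 1.3, the proportion of infants requiring an increase in respiratory support will be presented and compared using a Mantel-Haenszel statistic". EO-3 is a comparison "among infants in the vaccinated group who do / do not have apnea", so it does not compare randomized arms.

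**The concern.** There are two substantive gaps and one of wording.

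- **Gestational age.** The 8.4 count model adjusts for site alone and so does not follow the randomization, unlike the 8.2 and 8.3 models for the same measures. The expected cost is mainly precision.
- **No estimate of effect difference.** Readers of results split by PMA will ask whether the arm effect depends on PMA. Two p-values, one per group, cannot answer that. The protocol's rationale (1.2) is to support clinical decisions and future work on risk factors, so a spurious PMA pattern could mislead.
- **Wording.** SO1 is described as count data, but SOM 1.2 is a duration and SOM 1.3 a proportion. An analyst cannot tell whether those two belong in the PMA evaluation or, if so, by what method.

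**Working it through.** **Inputs.** From SAP 4.2: 135 per arm, 15% versus 30%, two-sided 0.05. The documents do not give the PMA split. I assume 50:50, 60:40 and 70:30, that is 68/67, 81/54 and 95/40 infants per arm.

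**1. The plan's own figure.** Power = Φ{[|p2−p1| − 1.96·√(2p̄(1−p̄)/n)] / √[(p1(1−p1)+p2(1−p2))/n]}. With p̄ = 0.225 and n = 135 this is Φ[(0.15 − 1.96×0.0508)/0.05] = Φ(1.01) = 84.3%, which reproduces the plan.

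**2. Discordant significance under one common effect.** Let a and b be the power in each PMA group. Then P(exactly one significant) = a(1−b) + b(1−a). With no effect this is 2×0.05×0.95 = 9.5%. At planned rates and 68/67, a = 0.554 and b = 0.548, giving 0.554×0.452 + 0.548×0.446 = 49.5%.

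| True rates, same in both PMA groups (unvaccinated vs vaccinated) | 50:50 | 60:40 | 70:30 |
|---|---|---|---|
| 15% vs 15% | 9.5% | 9.5% | 9.5% |
| 20% vs 16% (randomized trial in Protocol Table 2) | 16.8% | 16.8% | 16.9% |
| 15% vs 20% | 20.9% | 21.0% | 21.1% |
| 15% vs 22.5% | 31.9% | 32.1% | 32.7% |
| 15% vs 30% (planned) | 49.5% | 51.0% | 55.6% |

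In simulation, a Wald test of the difference between the two log odds ratios rejected in 3.9% to 4.6% of trials across these scenarios.

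**3. Precision of the ratio of odds ratios.** The variance of its log is the sum of 1/[n·p(1−p)] over the four arm-by-PMA cells. At planned rates the SE is 0.611 (50:50) to 0.669 (70:30). The 95% CI is the estimate divided and multiplied by exp(1.96×SE), a factor of 3.3 to 3.7. With no effect (15% in all cells) the factor is 3.8 to 4.3.

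These figures assume equal rates in both PMA groups. Protocol 1.1 says apnea is more frequent at lower gestational age. Take an odds ratio of 2.43 in both groups and let the older group be the smaller one. Assumed control rates of 20% (younger) and 8% (older) then give a factor of 3.8 to 4.7, and 22% and 5% give 4.6 to 6.3.

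**4. Interaction power.** If the planned effect (log 2.43 = 0.887) exists in one PMA group only and the other has 15% in both arms, the SE is 0.647 to 0.724. Power is Φ(0.887/SE − 1.96), about 23% to 28%.

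**5. Counts.** I simulated negative binomial counts with 15% of infants having any event, no arm or PMA effect, and assumed means of 0.3, 0.5 and 1.0 events. An arm-by-PMA test with model-based Poisson standard errors falsely rejected in about 24–26%, 44% and 63–64% of trials. With sandwich variance the rate was roughly 7% to 13%.

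**6. Which measures suit an arm-by-PMA ratio.** SOM 1.2 uses only infants with events. At planned rates that is 135×0.15 ≈ 20 and 135×0.30 ≈ 41, or 61 of 270, selected after randomization. In a PMA group of 40 per arm it is 6 versus 12. EOM 3.1 and 3.2 compare apnea with no apnea among vaccinated infants.

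**7. Overlap of gestational age with PMA.** Entry is at 6w0d to 12w0d postnatal age (Protocol 4.1). Reaching PMA 37w0d takes 37w0d − 27w6d = 9w1d for an infant born at 27w6d, and 12w0d, the last eligible day, for one born at 25w0d. The <28-week stratum may therefore be thin at PMA ≥37 weeks.

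**The case against.** **The wording may be harmless.** A reader might infer that 8.4 overrides 8.2 and puts a duration and a proportion into a Poisson model. The documents do not support that firmly. In the same paragraph EO2 stands for EO2.1 and EO2.2, and EO3 for EO3.1 and EO3.2, so SO1 is probably shorthand for SOM 1.1. What stands is that SOM 1.2 and SOM 1.3 are left without a stated place.

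**The SAP never says it will read discordant p-values as a PMA difference.** That is correct, and SAP 5.2 openly leaves secondary and exploratory analyses unadjusted. The 9.5% is what any two independent tests at 0.05 produce. The figures show what such results could not establish; they do not show an error the plan commits.

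**PMA may itself be the stratum.** Because the strata are unnamed, the wording could mean one odds ratio pooled over PMA. No discordance would then arise, and the figures in step 2 would not apply. This stands as a condition on them.

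**Gestational age may have been dropped on purpose**, since PMA contains it. That is possible, but the SAP does not say so. Two PMA groups do not replace the <28/≥28-week stratum. Protocol 6.2.2.3 and SAP 5.2 also mention site only, so the inconsistency is wider than 8.4.

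**The interaction estimate is weak**, and for counts a plain Poisson interaction would create false findings. Both points stand and shape the fix.

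**Conclusion.** The point holds as a weakness in a supporting analysis. SAP 8.4 omits a randomization stratum that 8.2 and 8.3 keep for the same counts, and it plans no estimate of whether the arm effect differs by PMA. Clarifying SO1 and the odds-ratio strata is mostly tidying.

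If PMA groups are tested separately, a single common effect of the planned size would leave exactly one group significant in about half of trials (49% to 56%), and no effect would do so in 9.5%. These figures rest on 135 per arm, equal rates in both PMA groups and assumed splits of 50:50 to 70:30. A reader might infer that the primary conclusion or the sample size is at risk, but neither depends on 8.4.

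**What to change.** In SAP 8.4:

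1. Stratify or adjust by site and gestational age (<28, ≥28 weeks) within PMA group, as in 8.1 to 8.3. State that results are given separately for each PMA group, and name the strata of the odds ratio.
2. For PO1, SOM 1.1, SOM 1.3, SOM 2.1, EOM 2.1 and EOM 2.2, and for SOM 2.2 only if events allow, add an arm-by-PMA ratio of effects with 95% CI, labelled exploratory. For binary measures, use the ratio of the two group-specific Mantel-Haenszel odds ratios, with variance equal to the sum of the variances of the two log odds ratios. For counts, use an arm-by-PMA term with sandwich variance or a negative binomial model, not model-based Poisson standard errors.
3. Replace SO1 in the count sentence with SOM 1.1. State that SOM 1.3 uses Mantel-Haenszel and that SOM 1.2 is descriptive only by PMA.
4. Keep EOM 3.1 and 3.2 descriptive by PMA, because they do not compare arms.

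**Cost.** SAP wording and one ratio per listed measure; no new data. The ratio will be imprecise: at best a factor of 3.3 to 3.7 each way at planned rates, and wider if apnea is rarer in the older PMA group. Robust variance remains somewhat liberal when few infants have events, and <28-week strata may be thin at PMA ≥37 weeks. The SAP should say that a non-significant interaction is not evidence of equal effects.
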